10.3 Final Analysis Plan

Aim 1 hypotheses will be tested via RM-ANOVA models. Bone strength index at the tibia and bone mass distribution at the hip, the dependent variables of interest, will be measured at 6-month intervals (0, 6, and 12 months). A significant time*group interaction would indicate that the two groups being compared in each model have significantly different changes in bone structure over 12 months. Huynh-Feldt corrected F-tests will be used in order to account for any possible violation of sphericity. It is hypothesized that the exercise group will have significantly greater improvements than the control or risedronate groups. Up to 20% attrition may be expected over the course of the study, but we expect it

to be less due to the use of cognitive behavioral strategies by Research Project Coordinators (RPC), the Research Exercise Trainer (RET), and ETs to promote exercise adherence and retention in the study. The method of handling missing data is not likely to have an effect with small amounts of missing data. However, If there is a higher than expected attrition rate, a maximum likelihood estimation method (e.g. mixed models) will be used instead of RM-ANOVA in order to utilize all available data and not delete cases in a listwise manner.

Hypothesis 2a compares the groups changes in BMD and will also be analyzed using RM-ANOVA. Hypothesis 2b also involves BMD, but assesses the proportions of preservation of BMD in each group. It is expected that at least 80% of subjects in both the exercise+ and risedronate+ groups will have preserved BMD at the three skeletal sites, and that the control/CaD group will have a significantly lower proportion of participants preserving BMD over 12 months. In order to classify individuals into preserved vs. declined groups, change in BMD over 12 months will be compared to the least significant difference as defined by the Hologic DXA manufacturer for each respective skeletal site. Differences of proportion of preservation across groups will be assessed via chi-square tests, which would indicate if preservation of BMD was significantly different across groups. Aim 3 investigates the changes in bone formation and resorption over 12 months also using repeated-measures ANOVA. Alkphase B and Serum NTx will be measured at baseline, 6, and 12 months.

The relationships of interest in Aim 4 will be explored by assessing the correlations between percentage of sessions attended, percentage of risedronate pills taken, and 12-month changes in bone structure at the tibia and hip. Assuming the variables are normally distributed, Pearson correlations will be used. Spearman rank correlations will be used if any of the variables are found to be non-normal.

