10.2 Sample Size Considerations

A power analysis was conducted for the primary aim of the study since it involves the most complex analysis. Hypothesis 1a states that at 12 months, there will be significantly greater improvements in BSI at the 4% tibial site in subjects in the exercise group compared to subjects in the control or risedronate groups. Power for the repeated measures analysis of variance (RM-ANOVA) was determined using G*Power3.1.5. A within-between interaction will be the primary test of significance (time*group interaction). It is assumed that the exercise group will have significantly greater improvements in BSI than either the control or risedronate groups. Two groups were assumed for the purposes of the power analysis because the control and risedronate groups will be compared to the exercise group separately. The total sample size will then be the number determined plus one half to populate the three groups. We investigated effect size evidence from similar studies and a variety of effect sizes was observed. However, effect sizes were not reported in the studies that were deemed most similar to the planned study. This study compares an exercise group to control and risedronate groups, which is unique so a large expected effect size could not be assumed without further evidence. Therefore, a small effect size was assumed for this power analysis ($f=.10$; Cohen 1992). Assuming a significance level of .05, 3 time points, and an estimate of .5 for the correlation between time points, 246 participants (82 per group) would be needed to have 80% power.

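### Section 10.3 analyses the month-0 value as an outcome and does not adjust for it; the test is valid but loses 11–33% of the effective sample at the plan's correlation of .5, depending on when the effect appears

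*Combined protocol and SAP*

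**What the plan says.** Section 10.3 states that "Aim 1 hypotheses will be tested via RM-ANOVA models" and that "the dependent variables of interest, will be measured at 6-month intervals (0, 6, and 12 months"). A significant time*group interaction is read as a difference in change between the two groups in the model. The same method carries over to the secondary outcomes: "Hypothesis 2a compares the groups changes in BMD and will also be analyzed using RM-ANOVA", and Aim 3 also uses repeated-measures ANOVA.

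Section 10.2 powers that test: "A within-between interaction will be the primary test of significance (time*group interaction"). It uses a small effect, f = .10, and continues: "Assuming a significance level of .05, 3 time points, and an estimate of .5 for the correlation between time points". "Two groups were assumed for the purposes of the power analysis", and the result is scaled by one half to fill three arms: "246 participants (82 per group) would be needed to have 80% power".

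Sections 10.2 and 10.3 name no baseline covariate and no constraint on the month-0 group means. A mixed model is planned only if attrition exceeds expectation, and its treatment of baseline is not described. In Section 3.1, H1a, H1b, H2a, H3a and H3c all refer to 12 months. On the timing of the effect, Section 4 says only that the largest difference is expected at 12 months.

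**The concern.** Month 0 precedes the interventions. DXA and the stored serum come from screening (Section 7.2), and the baseline pQCT is done at the enrolment visit (Section 6.4.4). With randomised groups the expected difference at month 0 is zero. The time*group interaction estimates that difference anyway, so its sampling error enters every contrast with later visits. Conditioning on each woman's own baseline removes that noise and corrects for chance imbalance. The design does not control such imbalance, because the protocol summary stratifies by exercise at baseline and not by bone values.

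What is at stake is precision on the primary hypotheses and most of the secondary ones, and some protection if attrition exceeds the planned 20%.

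**Working it through.** **Inputs.** From Section 10.2: alpha .05, m = 3 time points, rho = .5, f = .10, k = 2 groups per model, 82 per group (N = 164 per pair). Assumptions added here: unit variance, equal correlation between visits, and a range of effect profiles, since the documents give no 6-month effect. Write d6 and d12 for the standardised group differences at months 6 and 12.

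**1. The plan's own figure.** Noncentrality lambda = f² × N × m / (1 − rho) = .01 × 164 × 3 / .5 = 9.84. With 2 and (164 − 2) × 2 = 324 df, power is .805. 164 × 1.5 = 246, which matches the plan.

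**2. Information in each analysis at rho = .5.** Lambda is N/4 = 41 times a quadratic form in (d6, d12):

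- Planned interaction: A = (4/3)(d6² − d6·d12 + d12²).
- Joint 2-df test of group at months 6 and 12 given baseline: B = 1.5·d6² + 1.5·d12² − d6·d12. The residual covariance given baseline has variance 1 − .25 = .75 and covariance .5 − .25 = .25.

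The share of effective sample lost is 1 − A/B. Each profile is scaled so that the planned test keeps lambda = 9.84.

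| Profile (d12 = 1) | A | B | Loss | Adjusted lambda = 9.84 × B/A | Power at 82 per group |
|---|---|---|---|---|---|
| d6 = 0 | 1.333 | 1.500 | 11.1% | 11.07 | .85 |
| d6 = 0.25 | 1.083 | 1.344 | 19.4% | 12.21 | .89 |
| d6 = 0.5 (linear) | 1.000 | 1.375 | 27.3% | 13.53 | .92 |
| d6 = 1 (complete by month 6) | 1.333 | 2.000 | 33.3% | 14.76 | .94 |

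Simulation with 5,000 runs per cell agrees. Planned against adjusted power was .803 and .843 (d6 = 0), .806 and .913 (linear), .812 and .931 (complete by month 6). For 80% power the adjusted test needs about 73, 60 or 55 completers per group for these three profiles, against 82.

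**3. Month 12 alone.** The variance is 2(1 − rho) = 1.00 for the change score and 1 − rho² = .75 for the adjusted value, a loss of 25% whatever the profile. On the same scaling, d12² = .24/A, which is .24 (linear) or .18 (d6 = 0, or complete by month 6). The adjusted 1-df month-12 test then has lambda = 41 × .24/.75 = 13.12 (power .95) or 41 × .18/.75 = 9.84 (power .88). Both exceed .805.

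**4. Other correlations (assumed range).**

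| rho | Loss: d6 = 0 | Linear | Complete by month 6 | Planned lambda | Planned power |
|---|---|---|---|---|---|
| .5 | 11.1% | 27.3% | 33.3% | 9.84 | .805 |
| .7 | 5.9% | 15.8% | 20.0% | 4.92/.3 = 16.4 | .96 |
| .9 | 1.8% | 5.1% | 6.7% | 4.92/.1 = 49.2 | above .99 |

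**5. Why the replacement test must be named.** If month 0 is dropped but the group-by-visit interaction is kept as the test, it becomes a 1-df comparison of month 12 with month 6. Under the linear profile d12 − d6 = .245, so lambda = 41 × .06 / 1.00 = 2.46 and power is about .34. If the effect is complete by month 6, power is .05, the alpha level.

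**The case against.** The case for leaving the plan alone has four parts.

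- **The test is sound.** The interaction is valid under randomisation, suits aims worded as change, and reproduces 246 exactly. This stands: the point concerns efficiency only. It is no reason to keep the model, because under randomisation the adjusted difference at month 12 estimates the same quantity as the difference in change, with less variance.
- **The size is uncertain.** A reader might infer that the correlation of .5 by itself implies a loss of 27–33%. It does not. That range also needs a 6-month effect at least half the 12-month effect, which the documents do not give. The upper end fits poorly with their expectation of a maximum at 12 months. The .5 is itself a planning estimate; at higher values the gain in power is negligible at this f. This objection stands in full and sets the range reported here.
- **Baseline may not exist for everyone.** A reader might assume that every randomised woman has a baseline value. For BSI, Section 6.4.4 places the pQCT after the envelope is opened and the group read aloud. A woman who leaves at that moment has no baseline BSI, and such losses could differ by arm. Bone does not change within a visit and Section 6.1 blinds the outcome assessors, so adjustment still works. The caveat belongs in the plan.
- **The mixed-model fallback already covers this.** It does not. It is triggered only by excess attrition, and a mixed model with unconstrained month-0 group means keeps the same inefficiency.

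**Conclusion.** The point holds as a free improvement. The planned RM-ANOVA spends information on a month-0 difference whose expected value is zero. At rho = .5 the cost is 11–33% of the effective sample over profiles with 0 ≤ d6 ≤ d12, about 27% if the effect builds linearly, and 25% for the month-12 contrast. The cost falls to 6–20% at rho = .7 and 2–7% at rho = .9; it shrinks as the correlation rises but does not reverse. These figures assume equal variances and equal correlations across visits.

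The documents do not support reading this as bias, an invalid test or a wrong sample size. Nor do they support cutting recruitment: the gain depends on a correlation and an effect profile that are not established.

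**What to change.** In Section 10.3, for H1a, H1b, H2a, H3a and H3c:

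1. Model the 6- and 12-month values with group, visit, group-by-visit, the woman's baseline value and baseline-by-visit. Alternatively, keep month 0 in the outcome vector with group means constrained equal there.
2. State the test. Use either the baseline-adjusted group difference at month 12, which matches the hypotheses as worded, or the joint 2-df test of group at months 6 and 12. The group-by-visit interaction alone must not be the test.
3. Keep the pairwise comparisons, alpha and N unchanged.
4. Say how a randomised woman without a baseline pQCT will be handled.
5. Apply the same treatment of baseline to the mixed-model fallback.

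The cost is a few sentences, settled before any unblinded analysis. No new measurements are needed, and the model spends only a few degrees of freedom.

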2.3 Potential Risks and Benefits

2.3.1 Potential Risks

Risk of muscle soreness or injury with exercises.

There may be temporary muscle soreness for up to two days following the initiation of, or increase in resistance training or bone loading exercises. Sudden forceful movements (seldom associated with progressive and monitored exercise programs) are the most common cause of musculoskeletal injury associated with exercise. In the previous R01 study, some exercise subjects (< 10%) did complain of temporary muscle soreness with initiation of exercises or increase in weights lifted. If subjects complained of discomfort beyond the expected muscle soreness, exercises were not performed until the discomfort resolved. When subjects resumed exercises, they began with adapted exercises and lighter weights after another session with the YMCA Exercise Trainer (YET). No serious adverse effects occurred in the 110 subjects participating in exercises in the previous R01.

Important precautions have been specified for this protocol to minimize and decrease the likelihood of any risk associated with the exercise program. Precautions include formulation of specific inclusion and exclusion criteria and monitoring of subjects for safe performance of exercises. In addition, the exercise program is initiated slowly and gradually, and the estimated 1 repetition maximum (1 RM) testing is not completed until week 2, providing the body time to acclimate to strength training before the max testing is performed. If subjects complain of discomfort or pain from the exercise program (more than the expected muscle soreness) the on-site YETs will seek consultation with the Research Exercise Trainer (RET) and [name], Physical Therapist, and if necessary, refer subjects to their health care provider. The RET and [name], PT, will make the decision to discontinue the exercise program after consulting with the health care provider and considering the desires of the subject. Generally, subjects will not discontinue exercises because of musculoskeletal problems, but this would be dependent on the nature and severity of the problem and the desires of the subject. If the musculoskeletal problem and/or persistent pain is/are not resolved, the subject may discontinue the exercise program. This subject will be considered off-protocol and will be asked to complete all tests and measurements as scheduled in alignment with intent-to-treat principles.

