5.4.2 Handling of Subject Withdrawals or Subject Discontinuation of Study Intervention

If taken off protocol for whatever reason, we will still ask subjects to complete all tests and measurements as scheduled in alignment with intent-to-treat principles. There will be no extra attempt made to replace the subject as attrition is accounted for in the total number recruited and consented.

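### At the expected attrition the primary analysis is complete-case, and the switch to maximum likelihood has no defined trigger; bias in either direction is possible if scan loss differs by arm

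*Combined protocol and SAP*

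**What the plan says.** Section 10.3 sets the primary method in one line: "Aim 1 hypotheses will be tested via RM-ANOVA models". The test is the time-by-group interaction with a Huynh-Feldt correction, in two-group models over baseline, 6 and 12 months. The same method is carried to bone density ("Hypothesis 2a compares the groups changes in BMD and will also be analyzed using RM-ANOVA") and to the turnover markers in Aim 3.

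On missing data, section 10.3 makes three statements:

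- "Up to 20% attrition may be expected over the course of the study", followed by a remark that the investigators expect less.
- "The method of handling missing data is not likely to have an effect with small amounts of missing data".
- "If there is a higher than expected attrition rate, a maximum likelihood estimation method (e.g. mixed models) will be used instead of RM-ANOVA", the reason being "in order to utilize all available data and not delete cases in a listwise manner".

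Elsewhere the protocol aims to keep measuring women who stop their intervention. Section 5.4.2 says "we will still ask subjects to complete all tests and measurements as scheduled in alignment with intent-to-treat principles", and section 2.3.1 says the same for women who stop exercising because of musculoskeletal problems.

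**The concern.** The default is not labelled complete-case, but the reason given for switching shows that it is. Repeated-measures ANOVA needs all three scans, so a woman with baseline and 6-month data but no 12-month scan contributes nothing, and neither does one who missed only month 6. Leaving out observed scans of randomised women sits badly with the intent-to-treat reasoning in sections 2.3.1 and 5.4.2.

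The switch point is also loose. It could be 20%, or the unstated lower rate that the investigators expect. The plan does not say whether attrition is counted overall, by arm, by outcome or by missed scan. The primary method is therefore settled after attrition is known.

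Because women who go off protocol are still to be scanned, the risk comes only from scans that are not obtained. A complete-case contrast is safe if that loss is unrelated to outcome, or related to it in the same way and at the same rate in both arms. Several features make arm-specific loss plausible, though they do not prove it:

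- Participants get feedback on bone density (section 6.3).
- DXA results go to providers, with particular concern for bone loss in controls (section 2.3.1).
- One ground for ending participation is specific to the exercise programme (section 5.4.1).
- Contact is more frequent in the Exercise arm (sections 6.2 and 6.4.6).

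At stake is the direction and credibility of the Exercise comparison.

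**Working it through.** **1. Design figures (sections 10.2 and Protocol Summary).** Inputs: f = 0.10, alpha .05, two groups, three time points, correlation .5. With λ = f²·N·m/(1−ρ) = 0.01 × 164 × 3 / 0.5 = 9.84, df1 = 2 and df2 = (164 − 2) × 2 = 324, power is 0.805 (0.7998 at N = 162). Then 164 × 1.5 = 246, as stated. For attrition, 246 / 0.8 = 307.5, so 308 against the 309 stated. The plan's figures reproduce.

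**2. How many women are dropped.** 309 × 0.20 = 61.8, leaving 82.4 per arm and power of about 0.81. If an assumed 2%, 5% or 10% of the other 247 women miss only the 6-month scan, the total dropped is about 67, 74 or 87, leaving 81, 78 or 74 per arm against the planned 82.

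**3. Yardstick.** If the group difference grows linearly to d at 12 months, f = d·√(mean[(g − ḡ)²]/4) with g = 0, 0.5, 1. That is f = d·√(0.1667/4) = 0.204d, so f = 0.10 corresponds to d of about 0.49 SD.

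**4. Simulation under no true effect.** Settings: 103 per arm, Exercise versus Control, correlation .5, SD 1, 6,000 trials per scenario. Unless stated, loss is 20% in each arm after month 6. The documents give no loss mechanism, so these are assumptions: logit P(lost) = a − b·z, where z is the standardised 6-month change, b = 0.5, 1.0 or 1.5, and a is set to give the stated rate. Where only one arm is selective, loss in the other is random. At 20% loss, the worst quartile of 6-month change loses 31% to 49% and the best quartile 11% to 3% as b rises. The test is the complete-case interaction F-test with Huynh-Feldt correction at a nominal 5%.

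| Assumed loss pattern | False positives | Complete-case bias, 12-month difference (SD) |
|---|---|---|
| Random | 4.9% | 0 |
| Same selection, same rate in both arms | 4.8–5.2% | 0 |
| Exercise only selective | 7.9–24.0% | +0.05 to +0.11 |
| Control only selective | 8.0–24.9% | −0.05 to −0.11 |
| Exercise only selective, half the loss random before month 6 | 6.0–10.5% | +0.03 to +0.07 |
| Exercise only selective, 10% attrition | 5.8–10.1% | +0.02 to +0.06 |
| Same selection, 10% Control and 30% Exercise loss | 7.7–19.9% | +0.05 to +0.10 |

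Further points, the first two at b = 1.0:

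- With the same selection in both arms and 15% Control against 25% Exercise loss: 7.7%, +0.04 SD.
- With correlation .8 and Exercise-only selection: 16.0%, +0.06 SD.
- Testing the 12-month change alone, one-arm selection gives 6.2–11.6%.

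**5. Maximum likelihood on the same data.** The 12-month value is regressed on the two earlier scans in women observed at 12 months, then averaged over all women. Bias is within 0.004 SD in every pattern in the table. The standard error is 0.964 to 0.968 of the complete-case value under random loss.

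**6. Large-sample check** (400,000 women per arm, b = 0.5 and 1.0). Exercise-only selection gives +0.05 to +0.09 SD. Poor responders leaving Exercise while good responders leave the comparator gives +0.10 to +0.17 SD. Random loss at unequal rates (30% and 10%) gives about 0. Maximum-likelihood bias stays within 0.01 SD.

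**7. Missing not at random.** If Exercise loss depends on the unseen 12-month change, complete-case bias is 0.10–0.23 SD and maximum-likelihood bias 0.06–0.16 SD.

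**The case against.** **The trigger has an implied number.** Twenty per cent stands just before the rule and is the rate the trial is sized on, so a natural reading is that the switch happens above 20%. This stands in part. But the plan also expects less than 20% and leaves the counting unit open, and an explicit 20% threshold would still leave complete-case analysis as the default below it.

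**The bias depends on invented mechanisms.** It does, and milder ones do little: selection in both arms (b = 1.0 and 0.5) at 20% loss gives 6.6% and +0.04 SD; b = 0.5 in both arms with 22.5% against 17.5% loss gives 4.8% and +0.01 SD. No section says women are told their tibial or hip-structure results, so selection on the primary outcome may be indirect, and the case is stronger for bone density. This lowers the likely size; it does not make the default safe.

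**The largest error rates belong to the omnibus interaction test.** The hypotheses in section 3.1 are framed at 12 months, where one-arm selection gave at most 11.6%. That is correct, but the interaction is the test that section 10.2 calls primary.

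**Small losses do little.** At 10% loss with weak selection the error rate is about 6% and the bias about 0.02 SD, so the plan's sentence on small amounts of missing data is roughly right there. It does not hold for stronger selection, or for the 20% that the plan allows.

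**Maximum likelihood is favoured by construction.** Loss in the main scenarios depends on observed data. When it does not, maximum likelihood keeps about two-thirds of the bias, which is why a separate sensitivity analysis is needed.

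**Conclusion.** The concern holds and should be fixed. At or below the expected attrition, Aim 1, hypothesis 2a and Aim 3 are analysed on complete cases, and the rule for leaving that method is not defined. The sample size is not in error.

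The possible bias with loss selective in one arm is 0.05 to 0.11 SD at 20% attrition, or about 10% to 22% of the 0.49 SD design effect, and 0.02 to 0.06 SD (about 4% to 12%) at 10% attrition. It can favour Exercise or count against it. It is nil if loss is random, or equally selective at equal rates; unequal rates alone do not cause it.

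These sizes rest on assumed loss mechanisms and, for the yardstick, on a linear time pattern. The reading of the plan and the preference for a likelihood-based primary analysis do not depend on them.

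**What to change.** In section 10.3:

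- Make the maximum-likelihood mixed model the primary analysis for Aim 1 at any attrition rate, and likewise for hypothesis 2a and Aim 3. Include all randomised women as assigned and all available visits, with an unstructured covariance.
- Delete the switch rule and the sentence saying that the missing-data method is unlikely to matter.
- Keep complete-case repeated-measures ANOVA as a sensitivity analysis.
- Preferably add a missing-not-at-random sensitivity analysis, such as a delta shift applied to missing 12-month values, and report missing scans by arm and visit.

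The cost is wording and a little more analysis work. The method is already named in the plan, recruitment stays at 309, and precision is the same or slightly better (standard error about 3% to 4% smaller under random loss).

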3 OBJECTIVES

3.1 *Study Objectives*

Our **long-term goal** is to contribute to the development of clinical practice guidelines for the promotion of bone health in postmenopausal women with low bone mass. Our **central hypothesis** is that improvements in bone health will be greater in subjects randomized to the Exercise group compared to subjects in either the Control or Risedronate groups.

Aim1: To compare Control, Risedronate, and Exercise group subjects on changes in bone structure at the tibia (bone strength index [BSI]: pQCT) and hip (femoral neck and shaft, intertrochanteric) (hipstructural analysis: [HSA: DXA]) at baseline, 6, 12 months.

H1a: At 12 months, there will be significantly greater improvements in bone strength index (BSI) at the 4% tibial site in Exercise subjects compared to subjects in either Risedronate or Control groups

H1b: At 12 months, there will be significantly greater improvements in bone mass distribution (HSA; centroid, mm) at the femoral neck in Exercise subjects compared to subjects in either Risedronate or Control groups

Aim2. To compare Control, Risedronate, and Exercise group subjects on changes in BMD at the total hip, femoral neck, and spine (DXA) at baseline, 6, and 12 months.

H2a: At 12 months, there will be significantly greater improvements in BMD at the total hip, femoral neck, and spine in Exercise and Risedronate subjects compared to subjects in the Control group

H2b: At least 80% of subjects in both the Exercise and Risedronate groups will have preserved BMD at the total hip, femoral neck, and spine.

Aim3: To compare Control, Risedronate, and Exercise group subjects on changes in bone formation and resorption at baseline, 6, 12 months. (formation: AlkphaseB, resorption: Serum NTx).

H3a: At 12 months there will be significantly greater decreases in serum markers of bone resorption (Serum NTx) in subjects in the Exercise and Risedronate groups compared to subjects in the Control group

H3b: At 12 months, mean Serum NTx levels for subjects in both Exercise and Risedronate groups will have decreased to levels considered at low risk for fracture (< 12.6 nmol BCE/L)

H3c: At 12 months, there will be significantly greater improvements in serum markers of bone formation (Alkphase B) in Exercise subjects compared to subjects in either Control or Risedronate group subjects

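### H2b's preserved-BMD proportion would be computed on women scanned at 12 months rather than on all women randomised, and the missing-data fallback does not cover it

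*Combined protocol and SAP*

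**What the plan says.** Section 3.1 states H2b for the groups as a whole: "At least 80% of subjects in both the Exercise and Risedronate groups will have preserved BMD", at the total hip, femoral neck and spine. Section 10.3 sets the classification rule: "change in BMD over 12 months will be compared to the least significant difference as defined by the Hologic DXA manufacturer", site by site. It then sets the test: "Differences of proportion of preservation across groups will be assessed via chi-square tests". It names no denominator or analysis set for H2b.

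Missing data are handled in the paragraph of 10.3 on Aim 1. The expectation is: "Up to 20% attrition may be expected over the course of the study", with the hope that it will be less. The plan then reasons: "The method of handling missing data is not likely to have an effect with small amounts of missing data". The one provision has a trigger, "If there is a higher than expected attrition rate", and an action: "a maximum likelihood estimation method (e.g. mixed models) will be used instead of RM-ANOVA".

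Other sections bear on who will be scanned:
- Section 7.2.2 schedules DXA at screening, 6 months and 12 months.
- Sections 2.3.1 and 5.4.2 ask women who go off protocol to stay in testing, and both sections cite intention-to-treat (2.3.1 in its text on musculoskeletal problems).
- Section 5.4.1 lets women withdraw at any time. It also lets an investigator end participation for an adverse event, or when laboratory values change so that medication is needed.
- Section 5.5 counts T-scores falling below -2.5 within attrition.

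**The concern.** The class depends on a 12-month measurement. Without that scan a woman is neither preserved nor declined, so by default she leaves both the percentage and the chi-square. The likelihood fallback does not help. It fits a model to continuous repeated measures and assigns no class to anyone. It also stays off unless attrition exceeds what was expected. Moving the continuous outcomes to mixed models would leave H2b where it is.

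An absolute figure such as 80% is sensitive to who remains in the denominator. If women whose BMD is falling are less likely to be scanned at 12 months, the observed proportion is too high. If that loss differs by arm, the comparison with Control moves as well. The scheduled 6-month DXA carries information on women who are lost later, and H2b makes no use of it.

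**Working it through.** **Inputs from the documents.** 103 women randomised per group (section 5.3); 20% attrition and 246 retained of 309 (Protocol Summary, Population); the 80% expectation (section 3.1).

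**The plan's own figures.** The documents give no sample size or power for H2b. The primary calculation in section 10.2 reproduces. For the RM-ANOVA interaction with f = 0.10, correlation 0.5, three time points and two groups, power is 0.7998 at N = 162 and 0.805 at N = 164. Then 164 × 1.5 = 246, or 82 per group. For attrition, 82 / (1 − 0.20) = 102.5, rounded up to 103 per group, or 309 in all.

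**Step 1: who can be classified.** At 20% attrition, 103 × 0.80 = 82.4. So 82 women per group have a 12-month DXA and 103 − 82 = 21 do not.

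**Step 2: bounds.** Let x be the preserved women among those scanned, m the women not scanned, and q the share of the m who in fact preserved BMD. The proportion among all randomised is (x + q·m) / 103, with q anywhere from 0 to 1. Take the smallest x that reaches 80% among those scanned.

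| Attrition | Scanned | Observed | q = 0 | q = 1 |
|---|---|---|---|---|
| 10% | 93 | 75/93 = 80.6% | 75/103 = 72.8% | 85/103 = 82.5% |
| 20% | 82 | 66/82 = 80.5% | 66/103 = 64.1% | 87/103 = 84.5% |

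The bounds need no assumption about q.

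**Step 3: intermediate cases.** The documents give no preservation rate for women who are lost, so every q here is an assumption. With 85% preserved among the 82 scanned:
- q = 0.60: (82 × 0.85 + 21 × 0.60) / 103 = 82.3 / 103 = 79.9%
- q = 0.40: (82 × 0.85 + 21 × 0.40) / 103 = 78.1 / 103 = 75.8%

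**Step 4: counting every unscanned woman as declined.** 80% of 103 is 82.4, so 83 preserved women are needed. Only 82 are scanned at 20% attrition, and 82/103 = 79.6%. Under this rule the figure cannot be reached even if every scanned woman preserved BMD.

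**Step 5: the between-group test.** The Control rate is also an assumption, so a range is shown, against 66/82 in a treated group (uncorrected Pearson chi-square). The last column counts unscanned women as declined in both groups.

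| Control preserved | Scanned women only | All 103 per group |
|---|---|---|
| 50/82 (61.0%) | p = 0.006 | p = 0.025 |
| 53/82 (64.6%) | p = 0.023 | p = 0.067 |
| 55/82 (67.1%) | p = 0.051 | p = 0.120 |

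The handling of missing scans can change the reading of the test. Whether it would do so in this trial cannot be known in advance.

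**The case against.** The strongest reply is that the protocol works to keep the relevant women in follow-up. Section 2.3.1 asks a woman who stops exercise for unresolved pain to stay in testing. It asks the same of Control and Exercise women who start a bisphosphonate. Section 5.4.2 extends this to anyone off protocol. A reader might infer that women who stop because of pain, drug intolerance or falling BMD drop out of H2b. The documents do not support that: stopping treatment is not the same as missing the 12-month scan. What remains is that a request does not secure a scan, that sections 5.4.1 and 5.5 leave room for outcome-related loss, and that the plan itself budgets for 20% non-completion.

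Other parts of the reply also stand. Twenty per cent is a planning maximum, and the lower bound of 64.1% requires that none of the 21 lost women preserved BMD. The 80% is worded as an expectation, with no test against it and no success rule. BMD is a secondary outcome (section 3.2.2), so the primary analysis and sample size are untouched. At attrition up to the expected level the fallback is off for the continuous outcomes too, so H2b is one instance of a wider gap. Finally, no section says when women are likely to be lost, so how many would have a 6-month scan is unknown.

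None of this supplies a rule for a woman without a 12-month DXA.

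**Conclusion.** The point holds for a secondary hypothesis. As written, H2b yields an observed-case proportion and an observed-case chi-square. The plan does not state that denominator. It follows from the classification rule and the absence of any other rule. The denominator is women scanned at 12 months, adherent or not.

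At the planning maximum, an observed 80.5% is compatible with 64.1% to 84.5% of the women randomised. At 10% attrition, an observed 80.6% is compatible with 72.8% to 82.5%. The plan's view that the handling of missing data hardly matters when little is missing is therefore not secure for a figure compared with a fixed 80%.

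A reader might go further and infer that selective loss would cause the 80% to be declared met, or that 79.9% or 75.8% is the true proportion. The documents support neither. They set no formal criterion on 80% and give no preservation rate for lost women, and they do not show that outcome-related loss would be the main source of missing scans. What they support is that such loss is possible and that H2b has no protection against it.

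**What to change.** In section 10.3, define the H2b analysis set as all randomised women and add a missing-data rule of its own:

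1. Multiply impute 12-month BMD at each skeletal site from arm, baseline BMD, 6-month BMD where available, and off-protocol or bisphosphonate-start status.
2. Classify each imputed value against the least significant difference already specified for that site.
3. Pool the proportions and the between-arm differences, and base any statement about 80% on the pooled estimate.
4. Report the observed-case result beside it, with the number scanned in each arm. Give the best-case and worst-case bounds as a sensitivity range only. Counting all missing women as declined must not serve as the test of the 80% figure, because at 20% attrition it cannot be met.

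The cost is a little more analysis work and no added visits, since the DXA scans are already scheduled. The imputation rests on a missing-at-random assumption given the listed variables, which the bounds help the reader to judge. The reported proportion may come out slightly less favourable.
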